## 4.9 Assessments

All assessments will be conducted according to the standard practice applicable at each participating site. Assessments to be collected during the registry are found below:

### Schedule of Assessments

	Consent*	Biopsy**	Surgery	Final Outcomes***
Patient Data				
Informed Consent	X			
Demographic information (age, height, weight, diagnosis)		X		
Neoadjuvant therapy (start and stop date)			X	
Device and Procedural Data				
Reflector insertion data (success, deployment within lesion or distance from lesion, depth of reflector, type of guidance used, number of reflectors used, type of lesion, reflector detection)		X		
Reflector detection (before incision or after incision)		X i	X	
Reflector retrieval (success, identification and retrieval duration)			X	
Operative time			X	
Adverse events (including device deficiencies)		X	X	
Scheduling Data				
Date of assessment		X		
Date of biopsy and insertion		X		
Date of surgery			X	
Satisfaction Assessments				
Radiologist assessment: ease of placement; ability to position reflector in desired location; scheduling flexibility; visibility on ultrasound/mammography; artifact (Tomo/MRI if applicable)				X ii
Surgeon assessment: ease of detection; ease of reflector removal				X ii
Participant satisfaction questionnaire			X iii	

Pathology Report data				
Margins (positive; close <2mm; negative >2mm)				X
Re-excision required (after surgery)				X
Excised tissue information				X

\*Performed prior to biopsy

\*\*Reflector insertion performed at time of biopsy

\*\*\*No additional participant visit; data recorded from pathology report

i If performed

ii Collected once per clinician at completion of registry

iii Window up to 2 weeks post-surgery (remote completion)

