### **4.2 Endpoints**

The primary endpoint is the number of patient visits to the breast center for invasive procedures from the time of biopsy to surgery. The primary endpoint will be compared to historical controls. It is expected that there will be a mean reduction of at least one (1) visit for invasive procedures.

The secondary endpoints are defined below:

1. Device success: percent successful localization, detection and retrieval.
2. Device safety: rate of device-related adverse events.
3. Procedural success: absence of close margins (<2mm), positive margins (tumor on ink) or requirement for re-excision.
4. Duration (days) from diagnosis to surgery and biopsy to surgery.
5. Radiologist assessment: ease of placement; ability to position reflector in desired location; scheduling flexibility; visibility on ultrasound/ mammography (immediate and late); artifact (Tomo/MRI if applicable).
6. Surgeon assessment: ease of detection; ease of device retrieval.
7. Participant satisfaction questionnaire: anxiety; convenience; pain; overall experience compared to expectation
8. Process improvement with implementation of same-day biopsy and SCOUT® Reflector placement.

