#### 4.7 Device Period

Insertion of the SCOUT® Reflector shall be conducted according to the IFU at the time of biopsy. The physician will follow regular clinical practice before and during the biopsy procedure.

SCOUT® Reflector may be inserted in a soft tissue biopsy site or a soft tissue site intended for surgical removal as per IFU and clinician decision. Additionally, as per clinician decision, more than one (1) SCOUT® Reflector may be inserted in a participant (bracketing) ensuring a minimum distance of 25 mm between Reflectors.

The data collected during the biopsy and reflector insertion will consist of the following:

- Patient demographic: age, weight, height and diagnosis
- Date of assessment
- Date of biopsy and insertion
- Reflector insertion data: success, deployment within lesion or distance from lesion, depth of reflector, type of guidance used, number of reflectors used, type of lesion
- Lot number(s) and model of the SCOUT® Reflector

- Reflector detection (if performed)
- Adverse events (if applicable)

The data collected during the surgery will consist of the following:

- Date of surgery
- Neoadjuvant therapy (if applicable): start and stop date
- Reflector detection: success before or after incision
- Reflector retrieval data: success, identification and retrieval duration
- Operative time: Time from beginning the detection to the time the lesion is removed from the breast.
- Participant satisfaction questionnaire: this may be completed by/collected from the participant up to 2 weeks after the surgery.
- Adverse events (if applicable)

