#### **4.8 Final Outcomes**

The assessment of procedure success is determined by the pathology report. This will not require an additional participant visit for the purposes of the registry. Participation will be considered complete following collection of the final outcomes and Participant satisfaction questionnaire.

The following data points will be recorded from the report:

- Excised tissue information
- Specimen size
- Margins: (positive, close, negative)
- Re-excision required (after surgery)
- Radiologist assessment (collected once per radiologist at completion of study)
- Surgeon assessment (collected once per surgeon at completion of study)

---

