3.2 Endpoints

Primary Endpoint: The number of patient visits to the breast center for invasive procedures from the time of biopsy to surgery.

Secondary Endpoint:

1. Device success: percent successful localization, detection and retrieval;
2. Device safety: rate of device-related adverse events;
3. Procedural success: absence of close margins (DCIS: <2mm), positive margins (tumor on ink) or requirement for re-excision.
4. Duration (days) from assessment to surgery and biopsy to surgery;
5. Radiologist assessment: ease of placement; ability to position reflector in desired location; scheduling flexibility; visibility on ultrasound/ mammography (immediate and late); artifact (Tomo/MRI if applicable).
6. Surgeon assessment: ease of detection; ease of device retrieval.
7. Participant satisfaction questionnaire: anxiety; convenience; pain; overall experience compared to expectation
8. Process improvement with implementation of same-day biopsy and SAVI SCOUT® placement.

[figure not shown]
4 Study Methods

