4.4 Study Assessments

	Consent*	Biopsy**	Surgery	Final Outcomes***
Patient Data				
Informed Consent	X			
Demographic information (age, height, weight, diagnosis)		X		
Neoadjuvant therapy (start and stop date)			X	
Device and Procedural Data				
Reflector insertion data (success, deployment within lesion or distance from lesion, depth of reflector, type of guidance used, number of reflectors used, type of lesion, reflector detection)		X		
Reflector detection (before incision or after incision)		X ⁱ	X	
Reflector retrieval (success, identification and retrieval duration)			X	
Operative time			X	
Adverse events (including device deficiencies)		X	X	

Scheduling Data				
Date of assessment		X		
Date of biopsy and insertion		X		
Date of surgery			X	
Satisfaction Assessments				
Radiologist assessment: ease of placement; ability to position reflector in desired location; scheduling flexibility; visibility on ultrasound/mammography; artifact (Tomo/MRI if applicable)				X ⁱⁱ
Surgeon assessment: ease of detection; ease of reflector removal				X ⁱⁱ
Participant satisfaction questionnaire			X ⁱⁱⁱ	
Pathology Report data				
Margins (positive; close <2mm; negative >2mm)				X
Re-excision required (after surgery)				X
Excised tissue volume/weight & specimen size				X

^{*}Performed prior to biopsy

^{**}Reflector insertion performed at time of biopsy

^{***}No additional participant visit; data recorded from pathology report

ⁱIf performed

ⁱⁱCollected once per clinician at completion of registry

ⁱⁱⁱWindow up to 2 weeks post-surgery (remote completion)

Identification of any number ranges for numeric endpoints along with their corresponding text descriptors.

- Continuous variables will be collected for: age, weight, height, operative time and adverse event rate, duration between events
- Categorical variables will be established for device success, procedural success, clinician assessment, participant satisfaction

5 Sample Size

No formal sample size calculation has been performed. Five hundred (500) participants will be included in this registry. This sample size has been selected to adequately support a multi-center experience reflective of the Canadian healthcare system and associated workflow.

Further, the Canadian Agency for Drugs and Technologies in Health (CADTH) assessed the evidence of STREAMLoc_Statistical Analysis Plan v1.0_30AUG2021

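### The documents disagree on whether the under-2 mm close-margin criterion is DCIS-only, and the DCIS-only version cannot be reliably scored because final surgical histology is not a named item

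*Protocol*

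**What the plan says.** **Definition.** SAP 3.2 gives "Procedural success: absence of close margins (DCIS: <2mm), positive margins (tumor on ink) or requirement for re-excision". The Protocol synopsis carries the same DCIS tag twice, under the endpoints and under the study schedule. Protocol 4.2 drops the tag: "Procedural success: absence of close margins (<2mm), positive margins (tumor on ink) or requirement for re-excision".

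**Margin field.** The Protocol's Schedule of Assessments sets the categories as "Margins (positive; close <2mm; negative >2mm", and SAP 4.4 repeats them. Neither mentions histology. SAP 7.1 names a single source for procedural success, the margin assessment on the Outcomes CRF.

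**Diagnosis.** Both schedules mark "Demographic information (age, height, weight, diagnosis" in the Biopsy column only. Protocol 4.7 lists "Patient demographic: age, weight, height and diagnosis" with the biopsy and insertion data, and SAP 7.4 treats diagnosis as a baseline variable.

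**Pathology items.** Protocol 4.8 and 4.9 take margins, need for re-excision and an undefined item on the excised tissue from the surgical pathology report; 4.8 adds specimen size. SAP 4.4 words the tissue item as "Excised tissue volume/weight & specimen size". None of these is named as histology. Protocol 4.8 also states: "The assessment of procedure success is determined by the pathology report".

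**The concern.** If the 2 mm criterion applies only to DCIS, a case with a clear margin under 2 mm fails when the lesion is DCIS and passes when it is not, provided no re-excision is needed. The margin category cannot separate these two cases. If the analyst follows SAP 7.1 and uses that field alone, a non-DCIS case with a clear margin under 2 mm is failed, contrary to SAP 3.2. If the analyst turns to the diagnosis recorded at biopsy, cases whose histology changes at surgery are put under the wrong criterion. If the criterion covers all lesions, histology is not needed, but then the synopsis and SAP 3.2 are wrong.

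At stake is the meaning of a reported success rate. Two analysts working from the same locked database could report different values for this endpoint, each citing the plan.

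**Working it through.** The documents state no procedural success rate, DCIS share, histology-change rate or close-margin rate, so there is no figure of the plan's own to reproduce. The check has two parts.

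**1. The texts side by side**

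| Place | Under 2 mm applies to | Histology needed to score? |
|---|---|---|
| Protocol synopsis (two places) | DCIS | Yes |
| SAP 3.2 | DCIS | Yes |
| Protocol 4.2 | No restriction | No |
| Margin row, Protocol 4.9 and SAP 4.4 | No restriction | No |
| SAP 7.1 derivation | Margin field only | Not provided for |

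Take a non-DCIS lesion with a 1 mm clear margin and no re-excision. The schedule records it as close. From that field alone it is a failure; under SAP 3.2 it is a success. No item named as surgical histology is listed that would correct the score.

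**2. Size, for illustration only**

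Inputs from the documents:
- 500 participants (Protocol 5.1).
- At most 10% without surgery (Protocol 5.2), so the per-protocol set is at least 500 × (1 − 0.10) = 450.
- Endpoints are analysed on that set (Protocol 5.3).

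Assumed inputs, none in the documents:
- DCIS share *s*: 10% to 30%. It is taken at biopsy in (b), and as the share of operated cases in (a).
- Share of biopsy-DCIS cases whose histology changes at surgery so that the DCIS criterion no longer applies, *u*: 10% to 30%.
- Share with a close but not positive margin and no re-excision, *c*: 5% to 20%. Cases needing re-excision fail under either reading and are left out.

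(a) All-lesion versus DCIS-only reading: cases that change status = 450 × (1 − *s*) × *c*.
- Low: 450 × 0.70 × 0.05 = 15.75, or 3.5 points.
- Middle: 450 × 0.80 × 0.10 = 36, or 8.0 points.
- High: 450 × 0.90 × 0.20 = 81, or 18 points.

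(b) DCIS-only reading, with biopsy diagnosis used in place of surgical histology: cases that change status = 450 × *s* × *u* × *c*.
- Low: 450 × 0.10 × 0.10 × 0.05 = 0.225, or 0.05 points.
- Middle: 450 × 0.20 × 0.20 × 0.10 = 1.8, or 0.4 points.
- High: 450 × 0.30 × 0.30 × 0.20 = 8.1, or 1.8 points.

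Part (b) counts biopsy-DCIS cases only; these would be wrongly failed. A case labelled invasive at biopsy and found to be DCIS at surgery would be wrongly passed. Such cases add to the number misclassified but partly offset the net shift in the rate.

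**The case against.** A reader might infer that the plan applies the margin criterion by the wrong diagnosis. The documents do not say so. No section makes the biopsy diagnosis select the criterion; success is tied to the surgical pathology report, and a site completing the margin field has that report in hand. The plan is silent on which diagnosis governs. This part of the objection stands.

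It does not remove the problem. The field's categories are set by millimetres, so a site that follows the schedule records the distance whatever the histology. If some of the 3 to 7 centers instead apply histology themselves, no listed item would show it.

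A reader might also infer that the error could not be repaired. That is not supported either. Source reports are kept in the participant's file (Protocol 6.3), inconsistent or missing data are queried (5.4), and key performance data are audited before lock, with possible access to medical records (6.5). Histology could be re-abstracted, at more effort than collecting it once.

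Three further limits stand:
- The Protocol's tissue item could include histology. Only the SAP narrows it, and that SAP (v1.0, 30AUG2021) predates the current Protocol (v3.0, 21FEB2023).
- Lesion type and a morphology classification are also listed (SAP 7.5), equally undefined. That diagnosis means core-biopsy histology is itself an assumption.
- The CRF was not available, so it may already hold the field.

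Finally, this is one of eight secondary endpoints in a registry that Protocol 5.3 describes as having no pass/fail criteria. That limits the consequence, but a descriptive rate still needs a single definition.

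**Conclusion.** The point holds as a contradiction in the endpoint definition together with a gap in the listed data. The documents give two scopes for the 2 mm criterion. The derivation in SAP 7.1 fits only the unrestricted one, and the DCIS-only version in SAP 3.2 cannot be reliably scored or verified from the items listed.

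The scope question is the larger part: 3.5 to 18 percentage points. Using biopsy diagnosis as a substitute is modest: 0.05 to 1.8 points in biopsy-DCIS cases, before partial offset from changes in the other direction. Both ranges rest wholly on assumed rates; only the 500 participants and the 10% ceiling come from the documents. Which scope is clinically right is for the sponsor to settle.

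**What to change.** 1. Reconcile the synopsis, Protocol 4.2, the margin rows of Protocol 4.9 and SAP 4.4, and SAP 3.2 so that they give one scope for the close-margin criterion.
2. Add final surgical histology (invasive, invasive with DCIS, DCIS only, other) to the pathology items in Protocol 4.8 and 4.9 and SAP 4.4, and to the Outcomes CRF if it is not already there. With the margin category, this allows the endpoint to be calculated under either scope once the scoring of mixed lesions is stated.
3. If the criterion is DCIS-only, name that field in the SAP 7.1 derivation in place of any reliance on the biopsy diagnosis, and state how the invasive-with-DCIS category is scored.

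The cost is one extra field from a pathology report already being abstracted, plus short text changes to the Protocol and SAP. For participants already entered, the field would have to be filled from retained source reports.

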#### 4.10 Participating Centers

Participating centers will be selected by the Sponsor. All required approvals will be confirmed by the Sponsor prior to initiation of a participating site [i.e., REB/IRB, ISO 14155:2020 requirements and 21 CFR Parts 50, 54 and 56 requirements (US centers only)].

It is anticipated that there will be 3-7 centers participating in this registry.

#### 4.11 Sponsor responsibilities

Merit Medical Canada has the overall responsibility for the conduct of the study, including assurance that the study satisfies international standards and the regulatory requirements of the relevant regulatory authorities.

The Sponsor will be responsible for:

- Selection of clinical investigators and sites: The Sponsor will select qualified investigators and facilities which have adequate study population to meet the requirements of the investigation.
- Training of investigators and site personnel and site monitoring: The training of the Investigator and clinical site personnel will be the responsibility of the Sponsor, or designee, and may be conducted during an investigator meeting, a site initiation visit, or other training sessions. Periodic monitoring visits will be conducted frequently enough to ensure that all clinical participant data are properly documented and that the study is properly conducted.
- Documentation: The Sponsor will collect, store, guard and ensure completion of all study relevant documents by the relevant parties.
  - Signed and dated CRFs
  - Records of any Serious Adverse Events (SAEs) reported to the Sponsor during the clinical investigation
- Any statistical analyses and underlying supporting data
- Final report of the clinical investigation
- Submitting Reports

- Maintaining Records: The Sponsor will maintain copies of correspondence, data, SAEs and other records related to the clinical study according to requirements set forth by ISO 14155:2020 and regulations.
- Monitoring: The Sponsor is responsible for monitoring the study to ensure compliance with ISO 14155:2020 and regulatory requirements.

#### **4.12 Investigator responsibilities**

- Protocol acceptance: Prior to starting enrolment of participants, the Investigator must read and understand this study protocol, and must sign and date the Protocol Signature page. The Site Agreement documents agreement to all conditions of the study protocol and agreement to conduct the study accordingly. This study will be conducted in accordance the Declaration of Helsinki and other applicable regulatory requirements and standards, and any conditions of approval imposed by the REB/IRB or regulatory authorities.
- Required documents: The following documents must be submitted to the Sponsor, or designee prior to participant enrolment:
  1. Signed Protocol Signature Page
  2. Recent ( $\leq$  2 years old) signed and dated English Curriculum Vitae (CV) of the Principal Investigator and co-investigators of the clinical site. The CV should clearly show the Investigator/co-investigators' qualifications and experience.
  3. Copy of the written confirmation of the REB/IRB regarding approval of the protocol including version number and date, ICF (including version and date) and other adjunctive participant material.
  4. List of voting REB/IRB members
  5. Signed Clinical Trial Agreement
- REB/IRB approvals and notifications: According to the local requirements, the Investigator must have all necessary approvals, including written approval from the REB/IRB of the clinical site prior to enrolling participants in the study. A copy of the written approval must be provided to the Sponsor.
  - Serious Adverse Event (SAE) reports as well as annual and final reports will be submitted to the REB/IRB as required.
- Obtaining informed consent: The Principal Investigator, or qualified designee, will obtain informed consent in accordance with the procedure described in this study protocol and the requirements of the REB/IRB.
- Medical care of participants
- Reporting requirements
- Audits / Inspections: In the event that audits/inspections are initiated by the Sponsor (or its designee) or national/international regulatory authorities, the Investigator must allow access to

the original medical records and must provide all requested information. In the event that audits are initiated by regulatory authorities, the Investigator will immediately notify the Sponsor.

## 5. Data Analysis & Statistics

### 5.1 Sample Size Calculation

No formal sample size calculation has been performed. Five hundred (500) participants will be included in this registry. This sample size has been selected to adequately support a multi-center experience reflective of the Canadian and US healthcare system and associated workflow.

Further, the Canadian Agency for Drugs and Technologies in Health (CADTH) assessed the evidence of a competitive device and noted the requirement for a cohort size greater than 200 in order to draw conclusions of effectiveness. It is estimated that this sample size will result in a robust data set.

### 5.2 Point of Inclusion

A patient is considered enrolled in the registry as soon as they:

1. Have provided signed consent agreeing to be part of this registry; and
2. Undergo the insertion of the SCOUT® Reflector at the time of biopsy

*Note- If a patient has given consent but the Reflector is not inserted at biopsy, the patient will not receive a participant number and will not be considered as enrolled in the registry. No patient data will be collected.*

The intent-to-treat (ITT) population includes all participants in whom the SCOUT® Reflector has been inserted. Any participants who have a reflector inserted and do not undergo surgery will be exited from the registry using a study completion form. The occurrence of this scenario is expected to be low ( $\leq 10\%$ ). Reasons may include:

1. Benign concordant biopsy results.
2. Participant death prior to surgery due to metastases.
3. Lesion is metastatic from another location.
4. Participant declines surgery.
5. Participant is ineligible for surgery.

The per protocol (PP) population will include all participants in whom a SCOUT® Reflector has been inserted and who subsequently undergo breast surgery.

Participation in the registry will be considered complete after surgery, documentation of surgical outcomes and completion of the Participant Assessment Questionnaire. This will be documented on a study completion form. It is expected the duration of each participant will be approximately  $<7$  months and will vary based on each participant's treatment plan.

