## **4. Registry Plan**

### **4.1 Objectives**

The primary objective of this registry is to demonstrate the utility of the SCOUT® Surgical Guidance system to improve workflow and efficiency in centers diagnosing and treating breast cancer. The secondary objective is to further evaluate the safety and performance of the SCOUT® Surgical Guidance system in 500 consented BI-RADS 4C/5 patients according to the IFU.

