#### **4.6 Inclusion Period**

Patients meeting all inclusion criteria and no exclusion criteria will be considered for inclusion into the registry. Each eligible patient will be informed about the registry by the Investigator or designate.

Prior to any data collection, the patient must be thoroughly informed about all aspects of the registry and must have signed the Research Ethics Board (REB) or Institutional Review Board (IRB) approved Informed Consent Form (ICF). Participants will be assigned a unique identifier for the registry upon enrollment.

No patient data, including adverse events will be collected in this period. A patient will be considered enrolled in the registry at the time of reflector insertion.

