### 7.3 Reporting of safety related events

Adverse events and DD will be collected from the time the reflector is inserted into the participant (at biopsy) to the time the reflector is removed at surgery (Device Period) or until a study completion form is completed. Any AE in this period, either serious, non-serious, whether deemed device-related or not, must be reported to the Sponsor immediately after the investigator or coordinator has become aware of its occurrence. Reporting of an AE or DD to the Sponsor should take place within 24 hours upon becoming aware of the event, but not later than 3 calendar days. All AE (serious or non-serious) and DD will be documented in the eCRF. The AE/DD eCRF page should be submitted to the Sponsor within 24 hours even if all of the information is not available at the time of the initial contact. Sponsor contact for reporting: .

The investigator will evaluate (S)AEs with regard to causality and seriousness.

Reporting of serious incidents to the regulatory authorities will be reported per local regulations:

- Incident means any malfunction or deterioration in the characteristics and/or performance of the SCOUT® Surgical Guidance system, including use-error due to ergonomic features, any inadequacy in the information supplied by the manufacturer and any undesirable side-effect.
- Serious incident means any incident that directly or indirectly led, might have led or might lead to any of the following:
  - Death of a participant, user or other person,
  - Temporary or permanent serious deterioration of the participant's, user's or other person's state of health,
  - Serious public health threat;

Safety related events, which require preventive or corrective measurements intended to protect participants, may have to be reported to the local REBs/IRBs. The Sponsor will notify all other involved sites to report to their respective REBs/IRBs according to their requirements. The Sponsor will report any (S)ADEs and DD(s) to Health Canada and US FDA as required and within stipulated timelines.

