6.2 Analysis Populations

A patient is considered enrolled in the registry as soon as they:

1. Have provided signed consent agreeing to be part of this registry; and
2. Undergo the insertion of the SCOUT® Reflector at the time of biopsy

Note- If a patient has given consent but the Reflector is not inserted at biopsy, the patient will not receive a participant number and will not be considered as enrolled in the registry. No patient data will be collected.

Participation in the registry will be considered complete after surgery, documentation of surgical outcomes and completion of the Participant Assessment Questionnaire. This will be documented on a study completion form. It is expected the duration of each participant will be approximately <7 months and will vary based on each participant's treatment plan.

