6.2.3 Safety Population

Adverse events will be collected and analyzed for all events categorized as procedure or device-related for all enrolled participants between the point of inclusion to completion of surgery.

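### As written, a failed insertion attempt that leaves no reflector is outside every analysis set, so the registry reports neither the failure nor its device deficiencies and adverse events.

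*Protocol*

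**What the plan says.** **Enrolment.** Protocol 5.2 requires both signed consent and insertion of the reflector at biopsy, and adds: "If a patient has given consent but the Reflector is not inserted at biopsy, the patient will not receive a participant number". Without insertion, SAP 6.2 likewise says that "the patient will not receive a participant number and will not be considered as enrolled in the registry. No patient data will be collected". Protocol 4.6 agrees: "A patient will be considered enrolled in the registry at the time of reflector insertion".

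**Analysis sets.** Under Protocol 5.2 the ITT "population includes all participants in whom the SCOUT® Reflector has been inserted". The per-protocol (PP) set adds the condition of later breast surgery. SAP 6.2.3 analyses safety "for all enrolled participants between the point of inclusion to completion of surgery".

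**Start of safety data.** The Inclusion Period runs until insertion, and Protocol 4.6 says of it: "No patient data, including adverse events will be collected in this period". Protocol 7.3 starts the collection of adverse events and device deficiencies when the reflector goes in.

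**What the registry sets out to measure.** The secondary objective in Protocol 4.1 is to "further evaluate the safety and performance of the SCOUT® Surgical Guidance system in 500 consented BI-RADS 4C/5 patients according to the IFU". Protocol 4.7 lists insertion success among the data items, and Protocol 4.2 includes successful localization in device success. SAP 7.1 takes device insertion success from the Inclusion CRF item on deployment within the lesion. Protocol 7.1 counts malfunctions and use errors as device deficiencies, and Protocol 7.2 makes every deficiency reportable, with or without an adverse event.

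**The concern.** Whether insertion worked is an outcome of using the device, yet it is also the condition for entering the registry. A patient who consents, has an attempt that fails and leaves without a reflector never passes out of the Inclusion Period. That patient has no number, no CRF and no place in any denominator. The text does not distinguish a patient in whom insertion was never attempted from one in whom it was attempted and failed.

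Two results are affected. Insertion success loses failures that belong in it. The deficiency count loses malfunctions and use errors that stopped deployment, which are events the protocol itself defines as reportable. Because no data are kept, a reader of the final report could neither correct the figures nor confirm that the loss is negligible.

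**Working it through.** The plan states no insertion-success rate, attempt-failure rate or sample size calculation, so there is no figure of its own to reproduce. The check has two parts: tracing one patient through the rules, and then the arithmetic.

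**1. Tracing a failed attempt that leaves no reflector**

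| Question | Rule | Result |
|---|---|---|
| Enrolled? | Protocol 5.2, SAP 6.2 | No |
| In ITT or PP? | Protocol 5.2, SAP 6.2.1 and 6.2.2 | No; both need an inserted reflector |
| In the safety population? | SAP 6.2.3 | No; enrolled participants only |
| Deficiency or adverse event collected? | Protocol 4.6 and 7.3 | No; collection starts at insertion |
| Recovered per reflector? | SAP 9 counts reflectors used | No; no data exist for this patient |

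**2. Direction for insertion success**

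Let n be the participants in a set, s the successes among them, and f the excluded failed attempts, all failures by definition. The reported rate is s/n and the all-attempt rate is s/(n + f). Since f ≥ 0, s/n ≥ s/(n + f). The gap is (s/n) × f/(n + f). This holds when the same base set is used on both sides: ITT against ITT plus failed attempts, or PP against PP plus failed attempts.

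**3. Size**

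n = 500 is the planned enrolment (Protocol 5.1). The values of f and s are assumptions.

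| f | All 500 succeed (reported 100%) | 475 of 500 succeed (reported 95.0%) |
|---|---|---|
| 1 | 500/501 = 99.8% | 475/501 = 94.8% |
| 5 | 500/505 = 99.0% | 475/505 = 94.1% |
| 10 | 500/510 = 98.0% | 475/510 = 93.1% |
| 25 | 500/525 = 95.2% | 475/525 = 90.5% |

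The only nearby figure in the documents is the complaint rate for inaccurate deployment in Protocol 9.3, 0 to 0.22% annually. Applied to 500 it gives 0.0022 × 500 = 1.1, close to the f = 1 row. It counts complaints rather than failed attempts, so it is a rough low anchor only.

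**4. PP against all attempts**

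PP also drops participants without surgery, expected to be at most 10%, so this comparison can go either way. Suppose 430 of 450 PP participants succeed, all 50 without surgery succeed, and f = 1. PP gives 430/450 = 95.6%, and all attempts give 480/501 = 95.8%, which is slightly higher. With f = 5 the order reverses: 480/505 = 95.0%.

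**5. Adverse event rate**

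Assume 5 of 500 enrolled participants with an event (1.00%) and f = 10:

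- no events in the failed attempts: 5/510 = 0.98%
- the same rate: (5 + 0.1)/510 = 1.00%
- events in half: 10/510 = 1.96%
- events in all: 15/510 = 2.94%

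The sign depends on whether failed attempts carry events more or less often than enrolled cases. The documents do not say.

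**The case against.** **The wording might include attempts.** Protocol 5.2 enrols patients who undergo insertion, which could mean the procedure rather than its result, and recording insertion success fits that reading. But the note in the same section turns on whether the reflector is inserted, and the ITT definition on whether it has been. If attempts were meant, the text needs to say so.

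**Other channels might catch these cases.** The screening/enrollment log in Protocol 8 may allow a count of patients who consented but were not enrolled. It is not said to record attempts, outcomes or events, and no analysis uses it. Incident reporting to authorities under Protocol 7.3 covers malfunction and use error, but does not bring the cases into the registry's results.

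**The effect may be very small.** This stands. The complaint rate in Protocol 9.3 points that way. Protocol 10.1 requires proctor sign-off at Canadian sites and selects established users in the US. The registry is descriptive, with no pass/fail criterion, and insertion success is not an endpoint named on its own.

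**Stronger readings that do not hold.** A reader might infer that insertion success is 100% by construction. It is not: off-target deployments in enrolled participants are still recorded (SAP 7.1), as is a failed reflector followed by a successful one in the same participant. A reader might infer that PP success always overstates the rate over everyone attempted, but the 95.6% against 95.8% example shows otherwise. A reader might also infer that the adverse event rate is understated, but its direction cannot be determined from the documents.

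**Conclusion.** The point holds for patients who leave biopsy with no reflector after a failed attempt. As written, a stated rule removes them from ITT, PP and the safety population. It also removes from the deficiency count any malfunction or use error that prevented their deployment, contrary to the sense of Protocol 7.1 and 7.2.

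Within one base set the overstatement of insertion success has a fixed direction and an unknown size. For 500 enrolled successes it is 0.2 points with one failed attempt and 4.8 points with 25. These counts are assumptions, and the low end is the more plausible on what the documents give. No direction is claimed for PP against all attempts or for the adverse event rate. The primary endpoint is not part of this point. The change is worth making because it costs little and would show whether the effect is negligible.

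**What to change.** - **Protocol 5.2, 4.6 and 7.3; SAP 6.2 and 6.2.3:** assign a participant number at consent plus attempted insertion, and start adverse event and deficiency collection at the start of the attempt.
- **CRF:** add a short page for failed attempts recording the outcome, any deficiency and any adverse event.
- **Denominators:** use attempts for insertion success and for device- and procedure-related safety.
- **Reporting:** give consented, attempted, inserted and operated counts, and separate insertions not attempted from those attempted and failed.

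The cost is a protocol and SAP amendment with REB/IRB approval, including a check that the consent form covers data after a failed attempt, plus a little more data entry. Insertion success may look slightly less favourable, and the safety figures possibly so.
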